5.2 Study setting & target population

Study settings: Orthopedics Department, Indus Hospital and Health Network.

Targeted Population: patients having knee/hip osteoarthritis scheduled for joint replacement of one or both sides.

5.3 Duration of study

12 months

8 patients per month will be enrolled

5.4 Trial Population:

Screening Criteria

After giving the informed signed consent, participants will have a detailed examination and will assess for eligibility as defined in inclusion/exclusion criteria.

5.5 Clinical contraindications

Not any

5.6 Excluded medications

Not any

5.7 Known allergy/sensitivity or any hypersensitivity to components of study drug(s) or their formulation

Not any

5.8 Active drug or alcohol use or dependence that would interfere with adherence to study requirements

Serious illness requiring systemic treatment and/or hospitalization within 3-4 days prior to entry

Not any

6 Study enrollment procedures including informed consent

Prior to commencing the study, protocol and protocol consent form will be approved by the institutional review board (IRB). Once the identification will be completed, details will be carefully discussed with the subject.

If the patient or representative will not be able to read and sign then informed, then it will be signed and dated by an impartial witness who will be independent of the Investigator. A witness who will sign and date the consent form will certify that the information in this form and any other written information had been accurately explained to and understood by the patient or his / her representative.

7 STUDY TREATMENT (OR INTERVENTION)

7.1 Regimens (or Intervention), Administration, and Duration

All patients will randomize into two groups,

Group A: 1 dose of IV Dexamethasone 10mg+ tranexamic acid (20 mg/kg);

Group B: 2 doses of IV Dexamethasone 10mg+ tranexamic acid 20 mg/kg.

In group A, 1 dose of 10 mg of intravenous dexamethasone and 20mg/kg of intravenous tranexamic acid administered at 10 minutes before surgery.

In group B, dose of 10 mg of intravenous dexamethasone and 20mg/kg of intravenous tranexamic acid administered at 10 minutes before surgery and then 10mg of intravenous dexamethasone will be again administered before incision closure.

7.2 Concomitant Medications

7.2.1 Required Medications: IV TXA 20 mg/kg

IV Dexamethasone 10mg

7.2.2 Prohibited Medications: not any

7.2.3 Precautionary Medications: not any

7.3 Treatment Compliance (adherence assessment)

Treatment compliance:

If patient will come on follow up visits at 1st and 4th week for outcomes assessment, after discharge.

Treatment non compliance:

If patient will not come on follow up visits at 1st and 4th week for outcomes assessment, after discharge.

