9 CRITERIA FOR DISCONTINUATION

9.1 Permanent Treatment Discontinuation

- Drug-related toxicity
- Requirement for prohibited concomitant medications .
- Not completion of treatment as defined in the protocol.
- Request by subject to terminate treatment.
- Clinical reasons believed life threatening by the physician, even if not addressed in the toxicity section of the protocol.

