9.2 Premature Study Discontinuation

- Failure by the subject to attend consecutive clinic visits at 1st week and 4th week after discharge.
- Request by the subject to withdraw.
- Request of the primary care provider if s/he thinks the study is no longer in the best interest of the subject.
- Subject judged by the investigator to be at significant risk of failing to comply with the provisions of the protocol as to cause harm to self or seriously interfere with the validity of the study results.
- A defined study endpoint reached.
- At the discretion of the IRB or investigator.

from which investigators will take data of C-reactive protein values in our study

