10.3 Determination of Sample Size and Power Calculation

The calculated sample size, using total blood loss is 25 in each group and after adding 20% dropout the sample size will be $25+5=30$ in each group. The sample size is calculated using following information.

$Z_{1-\alpha/2}$ Level of significance=95%

μ_1 Expected mean change in total blood loss in Group A=93.80

μ_2 Expected mean change in total blood loss in Group B= 95.98

δ_1 Expected standard deviation in group A=3.88

δ_2 Expected standard deviation in group B=2.82

$Z_{1-\beta}$ power of the study= 80%

sample size in a group(n)= 38

After adding 20% drop out $38+8=46$ in each group.

Total sample size will be 92

No of groups/arms in study:

Type of comparison:

Superiority comparison

Type of configuration:

Parallel designs

Level of significance (Alpha level): 95 %

Power: 0.8 or 80 %

Allocation ratio: 1:1

Underlying population event rate:

Almost 90 percent of population undergoing total joint replacement, whether uni or bilateral would show the positive clinical outcomes with the use of 2 doses of dexamethasone.

Effect size of therapy: the clinical guidelines shows that each group of clinical trial must have at least 30 participants, so effect size is 92 more than sample size calculated, drop out patients percentages added.

Estimated loss to follow-up or refusals: Based on previous work in this population, 20 % will be lost to follow up or drop out from the trial.

10.4 Underlying population event rate:

The population enrolled in previous studies undergoing total joint replacement, whether unilateral or bilateral showed the positive clinical outcomes with the use of dexamethasone with tranexamic acid.

10.5 Estimated loss to follow-up or refusals: Based on previous work in this population, 20 % will be lost to follow up or drop out from the trial.

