11.6 Follow-up of Discontinuations

The research team will complete all scheduled safety follow-ups with any patient who has prematurely terminated the trial because of a Serious Adverse Event, non-compliance with the protocol, or loss of eligibility, including definite contraindications

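### Section 7.3 defines treatment compliance as attending follow-up visits, so the adherence measure cannot show whether the second dexamethasone dose, the only contrast between the arms, was given

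*Protocol*

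**What the plan says.** Section 7.3 of the protocol carries the words adherence assessment in its heading and gives two definitions. Compliance: "If patient will come on follow up visits at 1st and 4th week for outcomes assessment, after discharge". Non-compliance: "If patient will not come on follow up visits at 1st and 4th week for outcomes assessment, after discharge". Neither mentions dexamethasone or tranexamic acid.

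Section 7.1 places all study drug in theatre. Both groups receive dexamethasone and tranexamic acid shortly before surgery. In Group B only, "then 10mg of intravenous dexamethasone will be again administered before incision closure". That second administration is the one planned difference between the arms.

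Three other sections touch the same ground:
- 9.1 lists as a reason for permanent treatment discontinuation: "Not completion of treatment as defined in the protocol".
- 9.2 lists as a reason for premature study discontinuation: "Failure by the subject to attend consecutive clinic visits at 1st week and 4th week after discharge".
- 11.6 promises safety follow-up for patients who left the trial early for reasons that include "non-compliance with the protocol, or loss of eligibility".

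**The concern.** A treatment compliance measure should say whether patients received what they were assigned. Here treatment is finished before the patient leaves theatre, so coming to clinic after discharge carries no information about it. The 7.3 rule can be wrong in both directions: it passes a patient who missed the dose under test and fails a patient who had everything assigned.

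What is at stake is interpretation. If the trial finds no difference between one dose and two, the first question will be whether Group B actually received two. The protocol's stated adherence measure cannot answer it. If the trial does find a difference, a compliance rate reported under 7.3 would be read as evidence of delivered treatment when it only shows who came back.

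**Working it through.** **1. The rules applied to the possible cases.** The central claim involves no arithmetic, so the sections are set side by side.

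| Patient | 7.3 | 9.1 | 9.2 |
|---|---|---|---|
| All assigned doses, attends both visits | Compliant | Not met | Not met |
| Group B, no second dose, attends both visits | **Compliant** | **Treatment not completed** | Not met |
| All assigned doses, attends neither visit | **Non-compliant** | Not met | Premature study discontinuation |
| All assigned doses, attends one visit only | Not compliant; may not fit the non-compliance wording either | Not met | Unclear, since the criterion speaks of consecutive visits |

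Row 2 shows the inconsistency between 7.3 and 9.1. Row 3 shows one event with two labels: a treatment failure in 7.3 and a study discontinuation in 9.2. Row 4 shows that the two definitions in 7.3 may not cover everyone.

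**2. How far attendance and exposure can part.** The inputs from section 10.3 are 46 per group and 20% loss. The fraction f of Group B that misses the second dose is not in the documents; 5%, 10% and 20% are assumed to show a range. Two further assumptions are that everyone lost misses the visits, and that attendance does not depend on dosing.

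- Compliant under 7.3 but not fully dosed: 0.80 × f × 46
- Not compliant under 7.3 but fully dosed: 0.20 × (1 − f) × 46

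| f | Compliance under 7.3 | Received second dose | Compliant, not fully dosed | Not compliant, fully dosed | Misclassified, of 46 |
|---|---|---|---|---|---|
| 0 | 80% | 100% | 0 | 9.2 | 9.2 |
| 5% | 80% | 95% | 1.8 | 8.7 | 10.6 |
| 10% | 80% | 90% | 3.7 | 8.3 | 12.0 |
| 20% | 80% | 80% | 7.4 | 7.4 | 14.7 |

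The second column never moves. At f = 20% the two rates coincide by chance, although about a third of Group B is misclassified (0.16 + 0.16 = 0.32).

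**3. Context only: what missed doses would do to power.** The planning inputs in section 10.3 are for blood loss ("Expected mean change in total blood loss in Group A=93.80"; Group B 95.98; SDs 3.88 and 2.82). With δ = 95.98 − 93.80 = 2.18 and α read as 0.05 two-sided:

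n = (1.960 + 0.842)² × (3.88² + 2.82²) / 2.18² = 37.997, so the stated 38 per group reproduces.

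If the effect shrinks in proportion to missed doses, power = Φ(δ(1 − f) / (SD × √(2/38)) − 1.960), with SD = √((3.88² + 2.82²)/2) = 3.392. For f = 0, 5%, 10% and 20% this gives 80%, 76%, 71% and 61%. A t-test calculation gives about one point less throughout (79%, 75%, 70%, 60%). These figures depend on an assumed f and on an outcome that is not among those in section 4.1. They show why exposure is worth measuring; they are not a consequence of the wording of 7.3.

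**The case against.** The strongest reply is that nothing shown acts on the 7.3 label. The protocol defines no per-protocol set, excludes nobody for non-compliance and plans no report of a compliance rate. Analysis sets are commonly left to a statistical analysis plan, which is not at hand. This stands. A reader might infer that the comparison will be biased by dropping patients lost after discharge while keeping those who missed a dose. The documents do not support that; it would follow only if a later analysis used the 7.3 definition to exclude patients.

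Second, 9.1 and 9.2 already separate incomplete treatment from missed visits, and neither they nor 11.6 refer back to 7.3. Section 11.6 speaks of compliance with the protocol, a wider term than treatment compliance. This also stands: it would be too strong to say that the 7.3 rule is applied elsewhere. But it does not rescue 7.3, the only section presented as the adherence assessment, which gives a different answer from 9.1 for the same patient.

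Third, a reader might infer that the delivered contrast will be unknown. That goes too far. The wording of 7.3 does not stop doses from being recorded, and the data forms listed in section 14 are not shown. It can be said only that the stated measure does not use dose receipt, and that the items listed for staff training in 11.2 do not include it.

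Fourth, a reader might attribute a loss of power to 7.3. Any such loss would come from missed doses, not from the definition, and rewording would not recover it. Staff give the drug intravenously in theatre, and the documents give no reason to expect any particular rate of missed doses.

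Last, recording each dose on the post-operative form would undermine the blinding in 10.1 and 11.4, because the nursing staff who collect the data (11.1, 11.2) would see whether a second dose was given. This stands, and it shapes the fix.

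**Conclusion.** The point holds as a defect in a stated rule, not as missing detail. Section 7.3 labels retention as treatment compliance, misclassifies patients in both directions, and cannot show whether the only difference between the arms was delivered. It is inconsistent with 9.1 and duplicates 9.2.

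On the protocol's own figures, up to about 9 of 46 patients per arm could be called non-compliant despite full treatment, if all of the assumed 20% loss shows up as missed visits. The opposite error, untreated patients counted as compliant, cannot be sized from the documents because no missed-dose rate is given.

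No bias in the main comparison is shown, and no power figure belongs in the conclusion. The change is worth making because the error is plain and cheap to correct, but the trial's validity does not turn on it.

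**What to change.** 1. In 7.3, define treatment compliance as receipt of the assigned study drug doses, as documented in the anaesthetic or theatre record.
2. Have this captured by unblinded staff in a record that the blinded data collectors cannot see, and not on the post-operative form they complete. Section 10.1 also lists anaesthesiologists as blinded, so 7.3 should name the role that extracts and holds this information.
3. Rename the present rule 'visit attendance' and report it separately as retention. Say how a patient who attends only one of the two visits is classed.
4. Reconcile 7.3 with 9.1 and 9.2 so that a missed dose and a missed visit each carry one label, and state in 11.6 which kind of non-compliance is meant.

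The cost is a few lines of text and a separate field with restricted access. The compliance figure may turn out less favourable, but it will describe treatment received. No dose, schedule or visit changes.

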8 CLINICAL AND LABORATORY EVALUATIONS

8.1. Timing of Evaluations

8.1.1 Screening: Screening will be done during pre operative evaluations, prior to the enrollment in study. In addition to data being collected on subjects who enroll into the study, demographic, clinical, and laboratory data on screening failures will be captured in a screening log and entered into the database.

8.1.2 Pre-Entry

Pre-entry evaluations will complete at 15 days after screening evaluations have been completed.

8.1.3 Follow-up

Follow up will take place at 1st and 4th week, after discharge.

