4.1 Primary Objective

To evaluate the effectiveness of peri operative intravenous 2 doses of dexamethasone in lower limb joint/s replacement surgeries on postoperative C-reactive protein, post operative fatigue, postoperative joint range, post operative pain during rest and weight bearing, and length of hospital stay.

4.2 Hypothesis:

If hypothesis will get confirmed, then the peri operative use of 2 doses of dexamethasone with intravenous tranexamic acid, reduces the postoperative C-reactive protein, post operative fatigue, pain during rest and weight bearing, and length of hospital stay and improves the post operative joint range of motion.

If hypothesis will not get confirmed, then the peri operative use of 2 doses of dexamethasone with intravenous tranexamic acid, will not reduces the postoperative C-reactive protein, post operative fatigue, pain during rest and weight bearing, and length of hospital stay and and will not improve the post operative joint range of motion.

5. Material and Methods:

5.1 Study Design:

Randomized controlled trial with 2 arms

Arm 1: GROUP A will receive 1 dose of dexamethasone (10mg) with tranexamic acid (20mg/kg), peri operatively .

Arm 2: GROUP B will receive 2 doses of dexamethasone (2*10mg) with tranexamic acid (20mg/kg), peri operatively.

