11.3 Records to be kept

Total 4 questionnaires will be provided for each subject to record the data pre and post operative 1st day, 1st and 4th week after discharge. Subjects will be identified by the patient medical record number (MR no).

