13 HUMAN SUBJECTS

IRB OF INDUS HOSPITAL AND HEALTH NETWORK

APPROVAL LETTER BY IRB-INDUS HOSPITAL

Expedited v2- IRB Approval letter.pdf

14. Data collection instruments

It includes 4 questionnaire forms per patient

Pre operative form:

PreOpt_EFFECTIVENESSOFPERIOPER.pdf

Post operative 1st day form

PostOp_EFFECTIVENESSOFPERIOPER.pdf

Post operative 1st week after discharge from hospital, form

1stWeekAfterDischarge_EFFECTIV.pdf

Post operative 4th week after discharge from hospital, form

4thWeekAfterDischarge_EFFECTIV.pdf

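### Both follow-up visits are timed from discharge, so if two doses shorten hospital stay as hypothesised, Group B is assessed earlier in its recovery than Group A

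*Protocol*

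**What the plan says.** Section 8.1.3 sets the schedule: "Follow up will take place at 1st and 4th week, after discharge". The same starting point appears in four other places:

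- Section 7.3 defines compliance by attendance at these visits and says what they are for: "If patient will come on follow up visits at 1st and 4th week for outcomes assessment, after discharge".
- Section 9.2 lists as a reason for leaving the study "Failure by the subject to attend consecutive clinic visits at 1st week and 4th week after discharge".
- Section 11.3 provides four forms to "record the data pre and post operative 1st day, 1st and 4th week after discharge".
- Section 14 titles the forms to match, for example "Post operative 1st week after discharge from hospital, form".

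Among the postoperative assessments, only the first-day form is tied to the operation. No section counts a follow-up visit from surgery.

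Length of stay is itself an outcome. The primary objective (4.1) includes "post operative pain during rest and weight bearing, and length of hospital stay", and the hypothesis (4.2) is that the two-dose regimen "reduces the postoperative C-reactive protein, post operative fatigue, pain during rest and weight bearing, and length of hospital stay" and also improves joint range. The introduction (section 1) likewise says that repeat dosing might shorten stay further.

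**The concern.** A follow-up clock should start at an event that treatment cannot move. Here it starts at discharge, which follows both doses (section 7.1 gives the second before incision closure) and which the trial expects treatment to bring forward.

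Pain, fatigue and joint range can be expected to improve as days pass after surgery. If Group B leaves hospital earlier, its week-1 and week-4 measurements fall earlier in recovery than those of Group A. The comparison then mixes the effect of the second dose with a difference in recovery time. The distortion runs against Group B and grows with any benefit on stay, so success on one listed outcome would hide part of the benefit on the others.

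**Working it through.** **Time offset.** Take the visits as day 7 and day 28 after discharge:

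- days from surgery to visit = stay + 7, or stay + 28;
- difference between arms = mean stay in A − mean stay in B = D, at both visits.

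For illustration, stays of 4 days (A) and 3 days (B) put the visits at day 11 against day 10, and at day 32 against day 31. With D = 0 there is no offset.

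**Number per arm.** Section 10.3 gives 38 per group before dropout. Its inputs are means of 93.80 and 95.98, SDs of 3.88 and 2.82, 80% power, and a significance level read as two-sided 5%:

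- difference = 95.98 − 93.80 = 2.18;
- common SD = √[(3.88² + 2.82²)/2] = 3.392;
- n = 2 × [3.392 × (1.960 + 0.842)/2.18]² = 38.0.

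The 38 is reproduced. It is used here only to set the standard error. The blood-loss effect plays no part in what follows.

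**Assumptions (not in the protocol).** D = 0.5 to 1.5 days. Recovery is locally linear, at 0.05 to 0.10 SD per day at week 1 and 0.01 to 0.03 SD per day at week 4.

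**Formulas.**

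- Bias = D × slope. Week 1: 0.5 × 0.05 = 0.025 to 1.5 × 0.10 = 0.15 SD. Week 4: 0.5 × 0.01 = 0.005 to 1.5 × 0.03 = 0.045 SD.
- Standard error of the difference = √(2/38) = 0.2294 SD.
- k = bias / 0.2294.
- Coverage of a 95% interval = Φ(1.96 − k) − Φ(−1.96 − k).
- Chance of a significant result against Group B when there is no true effect = 1 − Φ(1.96 − k), nominally 2.5%.
- Power for an outcome on which 38 per arm would otherwise give 80% = Φ(0.842 − k).

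| Visit and case | Bias (SD) | k | Coverage | False result against B | Power (from 80%) |
|---|---|---|---|---|---|
| Week 1, low | 0.025 | 0.109 | 94.9% | 3.2% | 77% |
| Week 1, middle (1 day × 0.075) | 0.075 | 0.327 | 93.8% | 5.1% | 70% |
| Week 1, high | 0.15 | 0.654 | 90.0% | 9.6% | 57% |
| Week 4, low | 0.005 | 0.022 | 95.0% | 2.6% | 79% |
| Week 4, high | 0.045 | 0.196 | 94.6% | 3.9% | 74% |

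The high rows need the largest stay difference and the steepest recovery together. The false-result column applies if stay is shortened but the outcome in question is not affected. The power column applies under the protocol's own hypothesis, in which both benefit.

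**After the change.** With visits counted from surgery, the scheduled offset is 0 days at both visits whatever happens to stay, and the 38 per group is unchanged.

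**The case against.** The strongest reply is that bias presupposes a target. The protocol consistently describes status one and four weeks after discharge, and a randomised comparison of that quantity is valid for that quantity. However, the objective and hypothesis are framed as postoperative recovery, and nothing in the protocol argues for time since going home as the quantity of interest.

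A second reply is that the size rests wholly on assumed figures, is modest in mid-range at week 1 and is small at week 4. That stands. The arms differ by one further dose, and the introduction says only that repeat dosing may reduce stay. This limits the weight of the point but does not remove the mechanism.

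A third is that stay is recorded, so an analysis could use actual days since surgery. This helps only in part. Under the present schedule, time since surgery is stay plus a constant, apart from visits that slip. Adjusting for it largely means adjusting for stay, which is itself an outcome that treatment is expected to change.

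The last is that counting from surgery has its own imbalances: setting (ward or clinic) and days already spent at home may differ by arm, and some patients would have to return soon after discharge. These are fair costs. The setting should be recorded. Days at home before a visit at a fixed time after surgery are a consequence of treatment and do not make the timing of the comparison unequal.

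**Conclusion.** The point holds, conditionally. If two doses shorten stay by D days, Group B is assessed D days earlier after surgery at both visits, and pain, fatigue and joint range are biased against it to the extent that they improve with time. The protocol does not allow the size to be calculated. Under the stated assumptions it is a fraction of a standard error: 0.11 to 0.65 at week 1 and at most 0.20 at week 4.

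This is a design choice that should be changed because the trial's own hypothesis predicts the bias and removing it is cheap. It does not invalidate the trial. Confidence is medium, since both the stay difference and the recovery rates are assumed.

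**What to change.** Count both follow-up assessments from the date of surgery, with one visit window for both arms. Make the wording agree in sections 7.3, 8.1.3, 9.2 and 11.3 and in the form titles in section 14. In 7.3 and 9.2 only the words that time the visits need to change. A patient still in hospital at the first time point is assessed on the ward with the same form. Record the actual days since surgery and the setting at each assessment.

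The cost is wording in five places and a different way of booking the same two visits, with no extra visits, no new forms and no change in sample size. The drawbacks are an occasional ward assessment and, for patients with longer stays, sometimes a return trip soon after discharge. The second matters somewhat where 20% loss is already expected (10.3). If discharge timing is kept, recording days since surgery would at least show the offset, but would not cleanly remove it.
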